6.3.5. Number of subjects and expected duration

The number of subjects required to be included in the clinical investigation was set to up to 25 eligible subjects, which includes any “roll-in” subjects and 20 subjects for analysis. The time needed to select this number (*i.e.*, the enrolment period) was initially estimated to be twelve (12) months, however due to the worldwide pandemic and impact it has had to study enrolment, the study recruitment and enrolment period will be extended. The enrolment period is extended to allow the full cohort of subjects which is anticipated to be by the end of October 2022.

Following enrolment in the clinical investigation, each subject’s participation to this post-market study is expected to last twelve (12) months.

Therefore, this post-market clinical study is expected to last approximately four years, from the actual starting date in December 2019.

6.4. Procedures

6.4.1. Overview

Patients should be followed at regular intervals during one year after the initial percutaneous deep vein arterialization procedure. The protocol follow-up schedule is intended to align with the standard of care as seen with patients who are treated with surgical bypass or endovascular revascularization. Visits and exams scheduled for this post-market study are presented in Table 5 below (keys: ■ mandatory, □ optional).

Table 5. Visits and exams

Exams	Baseline	Treatment	Week 02	Month 01	Month 02	Month 03	Month 06	Month 09	Month 12
Eligibility	■								
Demographics	■								
Infection status [†]	■								
Venous mapping [‡]	■								
Angiogram	■	■							
Ultrasound		Duplex		Duplex	Duplex	Duplex	Duplex	Duplex	Duplex
Medication	■	■	■	■	■	■	■	■	■
Creatinine	■								
Rutherford	■			■	■	■	■	■	■
Wifi	■			■	■	■	■	■	■
Wound pictures	■		■	■	■	■	■	■	■
Pain	■		■	■	■	■	■	■	■
Perfusion	□		□	□	□	□	□	□	□
Quality of Life	■					■	■	■	■
Adverse events		■	■	■	■	■	■	■	■

[†]Wound culture and/or blood analysis (WBC, CRP, ESR)

[‡]Phlebography, duplex ultrasound, MRV or CTV, depending on what is available

6.4.2. Screening and baseline

The subject screening and recruitment process will be performed by the site medical personnel and should follow the steps below:

1. Critical limb ischaemia patients with no endovascular or surgical treatment options (inclusion/exclusion criteria are aligned with the CE-marked indications/contraindications, as per the IFU) are initially identified by the site investigators
2. No-option patients meeting the LimFlow System indications and contraindications (as provided in the instructions for use since the LimFlow System is commercially available) can be scheduled for a percutaneous deep vein arterialization
3. Patients scheduled for a LimFlow intervention are asked whether they would be willing to participate to the study (to collect the data associated to the surgical procedure and standard of care follow-up).
4. Patients candidate to the study are subsequently enrolled, treated, and followed as per standard of care (the study protocol does not require more visits than what is considered standard of care)

[figure not shown]

Once the patients have agreed to participate to the study (*i.e.*, once the informed consent has been obtained), the following exams will be collected:

- Demographics, medical history, and peripheral assessment
- Infectious status, *i.e.*, wound culture and/or blood analysis (WBC, CRP, ESR)
- Venous mapping of the foot, *i.e.*, phlebography, duplex ultrasound, MRV, or CTV
- Arterial angiogram from the common femoral artery to the foot (two views)
- Serum creatinine level
- Rutherford classification
- WIfI (Wound – Ischaemia – foot Infection) classification
- Wound pictures and assessment
- Pain assessment
- Perfusion assessment (TcPO₂, ICG i.v. injection, white-light spectroscopy with laser Doppler, etc.—optional)
- Quality of Life (EQ-5D)
- Review of medications (antiplatelets/anticoagulants and antibiotics regimen)

A dedicated website (decidemedical.com platform provided by ClinFlows) will be used during the screening process to assess the eligibility of the candidates identified by the investigators. Baseline radiological images (*e.g.*, arterial angiograms, phlebography, duplex ultrasound, MRV, or CTV) as well as wound pictures should be uploaded by the investigators in order for the patients' eligibility to be confirmed. The eligibility screening process that will be followed for this post-market study is presented in detail on Figure 1 below.

Figure 1. Eligibility screening process for LimFlow cases

6.4.3. Treatment and discharge

A LimFlow representative will attend the interventions performed in order to assist the physician on technical issues as well as to ensure that treatment characteristics and potential complications are duly recorded.

Primary steps of the percutaneous deep vein arterialization intervention are described in Section 2.8 “*Medical procedures involved*” on page 10. Refer to the “*Instructions for Use*” for proper preparation and use of the devices.

In addition to the procedure images (angiography and/or ultrasound), the following intra-procedure parameters will be specifically recorded:

- Target artery and target vein
- Procedural steps
- Technical success
- Medical devices used
- Total procedure time
- Total fluoroscopy time
- Total volume of contrast media
- Any adverse event or device deficiency

Patients should receive adequate antiplatelet and anticoagulation therapy for a minimum of three (3) months post-procedure as per institution practice.

6.4.4. Follow-up visits

Sites shall maintain a contact log recording the attempted follow-up visits, scheduled at one month, three months, six months, nine months, and twelve months. If a patient is not able to be contacted within three phone calls, the site shall send a letter requesting response from the subject and contact the patient general practitioner in order to check on the patient’s condition. If the site or service receives no response, the patient may be considered lost-to-follow-up at that time.

Follow-up and wound care are to be performed on-site under direct supervision of a study investigator. Patient wounds should be treated in accordance with the TIME guidelines or following similar recommendations.¹¹⁻¹⁷ An arteriography should be performed in case of suspected stent graft occlusion, as per standard practice.

Day 015: two weeks

At 15 days post-treatment, subjects will be examined during a clinic visit and the following assessment will be performed:

- Wound pictures and assessment
- Pain assessment
- Perfusion assessment (TcPO₂, ICG i.v. injection, white-light spectroscopy with laser Doppler, etc.—optional)
- Adverse events
- Review of medications (antiplatelets/anticoagulants and antibiotics regimen)

Day 030: one month

At 30 days post-treatment, subjects will be examined during a clinic visit and the following assessment will be performed:

- Rutherford classification
- WIFL (Wound – Ischaemia – foot Infection) classification
- Wound pictures and assessment
- Pain assessment
- Perfusion assessment (TcPO₂, ICG i.v. injection, white-light spectroscopy with laser Doppler, etc.—optional)
- Duplex ultrasound
- Adverse events
- Review of medications (antiplatelets/anticoagulants and antibiotics regimen)

Day 060: two months

At 60 days post-treatment, subjects will be examined during a clinic visit and the following assessment will be performed:

- Rutherford classification
- WIfI (Wound – Ischaemia – foot Infection) classification
- Wound pictures and assessment
- Pain assessment
- Perfusion assessment (TcPO₂, ICG i.v. injection, white-light spectroscopy with laser Doppler, etc.—optional)
- Duplex ultrasound
- Adverse events
- Review of medications (antiplatelets/anticoagulants and antibiotics regimen)

Day 090: three months

At 90 days post-treatment, subjects will be examined during a clinic visit and the following assessment will be performed:

- Rutherford classification
- WIfI (Wound – Ischaemia – foot Infection) classification
- Wound pictures and assessment
- Pain assessment
- Perfusion assessment (TcPO₂, ICG i.v. injection, white-light spectroscopy with laser Doppler, etc.—optional)
- Quality of Life (EQ-5D)
- Duplex ultrasound
- Adverse events
- Review of medications (antiplatelets/anticoagulants and antibiotics regimen)

Day 180: six months

At 180 days post-treatment, subjects will be examined during a clinic visit and the following assessment will be performed:

- Rutherford classification
- WIfI (Wound – Ischaemia – foot Infection) classification
- Wound pictures and assessment
- Pain assessment
- Perfusion assessment (TcPO₂, ICG i.v. injection, white-light spectroscopy with laser Doppler, etc.—optional)
- Quality of Life (EQ-5D)
- Duplex ultrasound
- Adverse events
- Review of medications (antiplatelets/anticoagulants and antibiotics regimen)

Day 270: nine months

At 270 days post-treatment, subjects will be examined during a clinic visit and the following assessment will be performed:

- Rutherford classification
- WIfI (Wound – Ischaemia – foot Infection) classification
- Wound pictures and assessment
- Pain assessment

- Perfusion assessment (TcPO₂, ICG i.v. injection, white-light spectroscopy with laser Doppler, etc.—optional)
- Quality of Life (EQ-5D)
- Duplex ultrasound (Note: if previous ultrasound assessment revealed a total occlusion of the stent graft and no further intervention was performed or planned, duplex ultrasound assessment at this timepoint may be unnecessary. This will be handled on a case-by-case basis and will be discussed between the site and Sponsor ahead of the follow-up and documented accordingly.)
- Adverse events
- Review of medications (antiplatelets/anticoagulants and antibiotics regimen)

Day 360: twelve months

Finally, at 360 days post-treatment, subjects will be examined during a clinic visit and the following assessment will be performed:

- Rutherford classification
- WIfI (Wound – Ischaemia – foot Infection) classification
- Wound pictures and assessment
- Pain assessment
- Perfusion assessment (TcPO₂, ICG i.v. injection, white-light spectroscopy with laser Doppler, etc.—optional)
- Quality of Life (EQ-5D)
- Duplex ultrasound (Note: if previous ultrasound assessment revealed a total occlusion of the stent graft and no further intervention was performed or planned, duplex ultrasound assessment at this timepoint may be unnecessary. This will be handled on a case-by-case basis and will be discussed between the site and Sponsor ahead of the follow-up and documented accordingly.)
- Adverse events
- Review of medications (antiplatelets/anticoagulants and antibiotics regimen)

6.5. Monitoring plan

Under the supervision of LimFlow SA, monitors will conduct investigational site monitoring to ensure that all investigators are in compliance with the Declaration of Helsinki (“Ethical Principles for Medical Research Involving Human Subjects”, 18th World Medical Association General Assembly, Helsinki, Finland, June 1964), the standard ISO 14155:2020 (“Clinical investigation of medical devices for human subjects—Good clinical practice”), the Clinical Investigation Plan, and the Investigator’s Agreement. Sites and source documents will be monitored to ensure that completed CRFs match medical records and to resolve any differences. The monitors and LimFlow SA will evaluate circumstances where an investigator deviates from the Clinical Investigation Plan.

The monitor’s responsibilities include: maintaining regular contact with each investigational site, through telephone contact and on-site visits, to ensure that the investigational plan is followed; ensure that complete, timely and accurate data are submitted; ensure that problems with inconsistent and incomplete data are addressed; and that the site facilities continue to be adequate.

The monitor shall have access to the source documents and other information needed to ensure investigator compliance with the clinical investigation plan and applicable rules and regulations, and to assess the progress of the clinical investigation. The clinical investigators shall allow auditing of their clinical investigation procedures.

LimFlow SA will review significant new information and ensure that such information is provided to the investigators, and to the Ethics Committees and Competent Authorities, as appropriate.

7. Statistical considerations

7.1. Statistical design, method and analytical procedures

Subject demographics, baseline characteristics and medical history will be summarized descriptively. Mean and standard deviation will generally be reported for continuous variables; median and range may be reported instead if the data distribution is skewed. Frequencies and proportions will be reported for categorical variables.

The design of this post-market study (PMS) is mirroring that of the early feasibility study (EFS) conducted in the United States of America, allowing for both datasets to be pooled in order to perform a statistical analysis on a larger cohort of patients.

7.2. Sample size

In the absence of formal statistical hypotheses for this single-arm, post-market study, the planned sample size could not be derived statistically. It was however estimated that a cohort of approximately twenty (20) subjects would provide sufficient data in order to meet the objectives defined in the study.

7.3. Provision for an interim analysis

Interim analyses may be performed at any time if deemed necessary to fulfil the sponsor's or manufacturer's reporting requirements and/or update the evaluation of the side effects and of the acceptability of the benefit/risk ratio, as required in Council Directive 93/42/EEC of 14 June 1993 concerning medical devices.

7.4. Specification of subgroups for analysis

If relevant, subgroup analyses may be performed based on baseline or treatment parameters—Student's (or Wilcoxon's according to the normality of the distribution) and Chi-2 (or Fisher's) between-group tests will then be used for quantitative and qualitative parameters, respectively.

In particular, renal function characteristics at baseline (GFR value and/or dialysis status) may be used to define subgroups for the purpose of the analysis. Specifically, patients on dialysis are excluded from the early feasibility study (EFS), which will be taken into consideration when pooling datasets from both cohorts. Safety and effectiveness results from dialysis and non-dialysis patients will be compared.

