14.5. Emergency contact details

Serious adverse events and serious adverse device effects must be reported to the sponsor LimFlow SA. Contact details are as follows:

LimFlow SA
 [name]
Director of European Clinical Affairs
 E-mail: [contact]
 [contact]

15. Vulnerable population

Not applicable for this post-market study.

16. Suspension or premature termination of the investigation

In the event of unforeseen or increased risks to subjects encountered during the course of the study, LimFlow SA, the Ethics Committee, the Competent Authority, or the Investigator may decide to suspend or terminate the clinical study. Such decision would be made after discussion with all parties.

If the investigator terminates or suspends the study without prior agreement with LimFlow SA, he/she will promptly provide all details to the institution, LimFlow SA, and the Ethics Committee. If the investigation is terminated or suspended by LimFlow SA, the investigator will be promptly informed, who must then inform the Ethics Committee. If the Ethics Committee terminates or suspends the study, the investigator will promptly inform LimFlow SA with written explanation.

Subjects will continue to be followed per the clinical investigational protocol unless it has been determined by the investigator that the continued follow-up may jeopardize the rights, safety, and/or welfare of the subject.

17. Publication policy

The data generated by this clinical study are the property of the sponsor, and should not be disclosed without their prior written permission. These data may be used by the sponsor now and in the future for presentation or publication at sponsor's discretion or for submission to governmental regulatory agencies. The principal investigator may publish or present the study results with prior consent of the sponsor, but will not disclose confidential information. Prior to submission by a principal investigator for publication or presentation, the sponsor will be provided with the opportunity to review the submission for confidential information and accuracy. The possibility of a publication in a peer-reviewed journal will be sought.

18. Definitions

Amputation	Major amputation is defined as amputation of the index limb at the level above the ankle. Minor amputation is defined as amputation(s) of the index limb (including metatarsals) at the level below the ankle.
Amputation-free survival	Defined as the percentage of subjects with limb salvage and survival.

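### Section 7.4 has no provision for unequal variances: its t-test rule can run at about 1% to 15% instead of 5% in small unequal subgroups, but only if the groups' SDs differ (minor)

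*Combined protocol and SAP*

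**What the plan says.** Section 7.4 makes subgroup work optional: "If relevant, subgroup analyses may be performed based on baseline or treatment parameters". It then fixes the method: "Student's (or Wilcoxon's according to the normality of the distribution) and Chi-2 (or Fisher's) between-group tests", the first pair for quantitative variables and the second for qualitative ones. It names no normality test, threshold, variance check, unequal-variance version of the t-test, significance level or subgroup size.

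The same section singles out renal function as a possible grouping and then says, without a condition, "Safety and effectiveness results from dialysis and non-dialysis patients will be compared". Exclusion criterion E-9 in Section 6.3.2 leaves haemodialysis patients eligible, so both groups can occur. Section 7.1 foresees pooling with the US early feasibility study, and Section 7.4 notes that "patients on dialysis are excluded from the early feasibility study (EFS".

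On size, Section 7.2 judges that "a cohort of approximately twenty (20) subjects would provide sufficient data" and explains: "In the absence of formal statistical hypotheses for this single-arm, post-market study, the planned sample size could not be derived statistically". Section 18 gives amputation-free survival, the primary endpoint, as follows: "Defined as the percentage of subjects with limb salvage and survival".

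**The concern.** Student's two-sample test, in its usual meaning, pools the two variances and assumes that they are equal. A normality check does not look at that assumption. Two normal samples with very different spread pass the check and go to the test that is least suited to them. The pooled test is most sensitive to this when the groups differ in size, and a split of about 20 subjects may well be uneven. Pooling with the feasibility study adds subjects only to the non-dialysis group. If dialysis patients are already the smaller group, the imbalance grows.

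The error can go either way. If the smaller group is the more variable one, chance differences look significant too often. If the larger group is the more variable one, real differences are hidden. What is at stake is the credibility of p-values for quantitative subgroup comparisons. Section 7 names no other hypothesis tests than those in 7.4.

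**Working it through.** **Inputs from the documents.** About 20 subjects for analysis (Section 7.2); the Student's-or-Wilcoxon's rule (Section 7.4). The plan states no error rate for these tests, so there is no figure of its own to reproduce.

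**Assumptions.** Two-sided 5% level. Splits of 20 from 3 v 17 to 10 v 10, with 5 v 15 as the main illustration. Ratio r of the smaller group's SD to the larger group's SD from 0.5 to 3. Normality judged by Shapiro-Wilk at 5%. Student's read as the equal-variance test. None of these is given in the plan.

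**Step 1: why the size moves.** Set the larger group's SD to 1, with n1 = 5 and n2 = 15.
- True variance of the mean difference: r²/5 + 1/15.
- Variance that Student's test estimates on average: [(4r² + 14)/18] × (1/5 + 1/15).
- At r = 2: true = 4/5 + 1/15 = 0.867; estimated = (30/18) × 0.267 = 0.444. The quotient is 1.95, so the t statistic is too large by about √1.95 = 1.40. The critical value 2.101 (18 df) then acts like 2.101/1.40 = 1.50, and the two-sided tail of t with 18 df beyond 1.50 is about 15%.
- At r = 1 the quotient is 1 and the size is 5%.
- At r = 1.5: 0.517/0.341 = 1.52; effective cut-off 2.101/1.23 = 1.71; tail about 10.5%.
- At r = 0.5: 0.117/0.222 = 0.525; effective cut-off 2.101/0.725 = 2.90; tail about 1.0%.

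**Step 2: simulation at 5 v 15, normal data, equal means.** Student's and Welch's: 200,000 replicates per setting. Full rule (normality checked in each group, then Student's or Wilcoxon's): 12,000 replicates.

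| r | Student's alone | Rule in 7.4 | Welch's alone |
|---|---|---|---|
| 0.5 | 1.0% | 1.5% | 4.9% |
| 1 | 5.0% | 5.2% | 5.4% |
| 1.5 | 10.8% | 10.3% | 5.7% |
| 2 | 15.8% | 15.4% | 5.7% |
| 3 | 22.2% | 21.2% | 5.5% |

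The normality check barely changes the result, because about 90% of these samples pass it. Checking normality on the combined sample or on residuals gives 13.8% or 14.4% at r = 2.

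**Step 3: other splits, Student's alone at r = 2.** 3 v 17: 22.2%; 4 v 16: 18.6%; 6 v 14: 13.2%; 8 v 12: 8.7%; 10 v 10: 5.4%. For assumed pooled-dataset sizes, 5 v 40 gives 24.3% and 10 v 40 gives 18.3%.

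**Step 4: possible repairs.**
- Wilcoxon's alone, 5 v 15, r = 2: 8.0% to 9.3%.
- Adding a Levene pre-test to choose between Student's and Welch's: 10.7% to 12.0%.
- Welch's for everything, including skewed data: on exponential data with equal distributions, 6.6% to 9.7% at 5 v 15 and 4 v 16, against about 5% for the present rule.
- Welch's in place of Student's, with Wilcoxon's kept: 4.6% to 7.0% from 4 v 16 to 6 v 14, on normal and exponential data.

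The last option holds its level best across the cases tried.

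**The case against.** The strongest answer is that little depends on these tests. The primary endpoint is a percentage. The secondary endpoints that Section 18 defines (patency, limb salvage, technical and procedural success) are yes/no states. Under 7.4 all of these go to Chi-2 or Fisher's. Student's test reaches only variables outside the endpoint list, such as the pain rating and EQ-5D (Section 6.1.5) or procedure time, fluoroscopy time and contrast volume (Section 6.4.3). There are no formal hypotheses, and no decision is tied to any subgroup p-value. All of that stands, and it is why the priority is minor.

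It also stands that the simulated rule is partly an assumption: the plan does not name a normality test, and the equal-variance reading is inferred from the test's name.

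Three stronger readings are tempting and are not supported:
- A reader might infer that small unequal groups by themselves inflate the error to about 15%. They do not. The rate is about 5% with equal SDs, and the documents give no SDs from which to expect a ratio of 2.
- A reader might infer that the dialysis comparison, which is worded as definite, puts the main results at risk. That sentence concerns safety and effectiveness results, and no named endpoint clearly falls to Student's test.
- A reader might infer that Wilcoxon's should go too. Section 7.1 itself allows for skewed data, and there Welch's alone does worse than the present rule.

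**Conclusion.** The point holds in a limited form. Section 7.4 has a real gap: it selects Student's test on normality alone and says nothing about unequal variances. At an assumed 5 v 15 split and two-sided 5% level, the stated rule has a false-positive rate of about 1%, 5%, 10% and 15% when the smaller group's SD is 0.5, 1, 1.5 and 2 times the larger's. The effect depends on the SDs differing as well as the group sizes; at 10 v 10 it nearly vanishes. Pooling with the feasibility study cannot add to the dialysis group, so it would make an already smaller dialysis group relatively smaller still.

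The consequence is that exploratory p-values on quantitative variables may mislead. The primary analysis is not affected. Minor priority, justified by the low cost of the change.

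**What to change.** In Section 7.4, replace Student's test and keep the rest of the rule. Suggested wording: *Quantitative variables will be compared with Welch's (unequal-variance) t-test, with the 95% confidence interval of the difference; Wilcoxon's test will be used for clearly skewed or ordinal data. All subgroup results are exploratory.*

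Do not add a variance pre-test: with one, the rate at 5 v 15 and an SD ratio of 2 is still 10.7% to 12.0%. No change to how subgroups are defined is needed for this point.

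The cost is one sentence, with no new data and no change to conduct. There are two small statistical costs. Intervals are slightly wider when the variances really are equal. The error rate on skewed data rises slightly, to about 7% at 4 v 16. In the smallest groups Welch's is not exact either: at 3 v 17 it runs at 5.8% to 7.4% for SD ratios 0.5 to 2, against 0.4% to 22.2% for Student's.

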6.3.4. Criteria and procedures for subject withdrawal or discontinuation

Patients are withdrawn from study if signed informed consent is withdrawn or when lost to follow-up (if a patient is not able to be contacted within three phone calls, the site shall send a letter requesting response from the subject and contact the patient general practitioner in order to check on the patient's condition; if the site or service receives no response, the patient may be considered lost-to follow-up at that time). Early study exit will also occur if the patient reaches the primary study endpoint either in death, or major amputation of the treated limb. Reason for the study discontinuation must be recorded in the source documentation and on the electronic Case Report Form (eCRF).

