14.2. Reporting

All adverse events will be documented in the case report forms, including date of onset, symptoms, treatment, duration (or the fact that it is still continuing), resolution, and assessment of both the seriousness and the relationship to the device. Similarly, all device deficiencies will be documented in the case report forms. In addition, all serious adverse events and serious adverse device effects must be reported immediately after discovery by any site member to LimFlow SA.

LimFlow SA will report such an event and the results of an investigation to the appropriate regulatory authorities in compliance with applicable regulatory requirements. If LimFlow SA and the investigator determine that the events present an unreasonable risk to the subjects, LimFlow SA will terminate all or parts of the study.

The reporting of any serious adverse events and/or serious adverse device effects to the Ethics Committee is the sole responsibility of the site's Principal Investigator.

All adverse events will be adjudicated by the independent committee in order to assess the procedure or device relatedness as well as the event seriousness.

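### The dialysis comparison in section 7.4 has only yes/no tests for amputation-free survival, a dated first event, and no rule for subjects whose follow-up is incomplete

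*Combined protocol and SAP*

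**What the plan says.** Section 7.4 opens by making subgroup work optional: "subgroup analyses may be performed based on baseline or treatment parameters". It then allows Student's or Wilcoxon's for quantitative parameters and, for the rest, "Chi-2 (or Fisher's) between-group tests will then be used for quantitative and qualitative parameters, respectively". On dialysis the wording is firmer: "Safety and effectiveness results from dialysis and non-dialysis patients will be compared". It names no endpoint for that comparison. No Kaplan-Meier estimate, log-rank test, Cox model or censoring rule appears anywhere in section 7.

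Section 18 gives the form of the primary endpoint, amputation-free survival: "Defined as the percentage of subjects with limb salvage and survival". No timepoint is attached.

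The event and its date are both available. Section 6.3.4 states "Early study exit will also occur if the patient reaches the primary study endpoint either in death, or major amputation of the treated limb", and section 14.2 states "All adverse events will be documented in the case report forms, including date of onset".

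Some subjects will be only partly observed:
- Section 6.1.6 does not replace those who drop out or withdraw consent after the procedure.
- Section 6.3.3 follows subjects with no attempted or successful implantation for 30 days, or longer if a related adverse event is unresolved. It then exits them without replacement.
- Section 7.5 only counts missing data and shows subject accountability.

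On size, section 7.2 judges that "a cohort of approximately twenty (20) subjects would provide sufficient data". It adds: "In the absence of formal statistical hypotheses for this single-arm, post-market study, the planned sample size could not be derived statistically".

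**The concern.** The plan collects when each subject died or lost the limb, then offers only tests that ask whether it happened. That has two consequences.

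First, a subject who leaves event-free at day 30 or day 200 has no defined twelve-month status. The percentage, and any test built on it, then depends on an unwritten choice between dropping the subject, counting a success or counting a failure. In a small dialysis group, one such choice moves the result visibly.

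Second, the small-sample member of the yes/no pair, Fisher's, is strongly conservative at this size, so a real difference is less likely to be detected than with other tests on the same subjects.

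This is the only subgroup comparison the plan says will be made, and it concerns the sole primary endpoint.

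**Working it through.** **Inputs from the documents.** About 20 subjects for analysis (section 7.2) and twelve months of follow-up (section 6.1.1). The plan states no power, alpha, event rate, dropout rate or dialysis share, so it has no figure to reproduce.

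**Assumptions.** Two-sided 5%. Dialysis:non-dialysis splits of 5:15, 7:13 and 10:10. Twelve-month amputation-free survival mainly 70% without dialysis (60 to 90% also tried). Hazard ratio (HR) 2 to 10. Dropout 0% or 15%.

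**Step 1: what an undefined status does.** Take 7 dialysis subjects, of whom 3 have events, 3 complete event-free and 1 is lost. Amputation-free survival is 3/7 = 43% if the lost subject counts as an event, 3/6 = 50% if dropped, and 4/7 = 57% if counted event-free. One subject moves the estimate by 1/7 = 14 points. Coding also moves the test. At 10:10, HR 3 and 15% dropout, Fisher's power is 16.0% with dropouts counted event-free and 22.8% with completers only.

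**Step 2: which yes/no test would apply.** The smallest expected cell is (smaller group) x (smaller of events and non-events) / 20. With 20 subjects it cannot exceed 10 x 10 / 20 = 5, and it reaches 5 only with a 10:10 split and exactly 10 events. At 7:13 with HR 3, dialysis survival is 0.70^3 = 0.34. Expected events are 7 x 0.66 + 13 x 0.30 = 8.5, and the smallest cell is 7 x 8.5 / 20 = 3.0. Fisher's is therefore the likely choice, although section 7.4 gives no switching rule.

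**Step 3: true size at nominal 5%.** In simulation with exponential event times, Fisher's rejected in 1.0 to 2.5% of null trials, uncorrected Chi-2 in 3.1 to 5.3% and the ordinary log-rank in 4.2 to 5.0%. A second simulation (early events, Weibull shape 0.6, equal 65% survival) gave 1.6 to 3.7% for Fisher's and 3.5 to 5.6% for the permutation log-rank.

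**Step 4: power at 7:13, 70% survival without dialysis (%).** With 15% dropout, the yes/no tests count dropouts as event-free.

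| HR | Dropout | Fisher's | Chi-2 | Permutation log-rank | Gain over Fisher's | Gain over Chi-2 |
|---|---|---|---|---|---|---|
| 2 | 0% | 8.9 | 14.7 | 14.7 | 5.8 | 0.0 |
| 3 | 0% | 20.3 | 35.7 | 34.8 | 14.5 | -0.9 |
| 4 | 0% | 33.9 | 54.8 | 53.1 | 19.2 | -1.7 |
| 2 | 15% | 7.5 | 12.6 | 13.3 | 5.8 | 0.7 |
| 3 | 15% | 19.6 | 31.3 | 32.7 | 13.1 | 1.4 |
| 4 | 15% | 30.7 | 48.5 | 49.4 | 18.7 | 0.9 |

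The upper end comes from scenarios such as 10:10, HR 4, 15% dropout: 54.6 - 31.1 = 23.5 points. Across the simulations the permutation log-rank gains about 5 to 24 points over Fisher's and between -3 and +9 over uncorrected Chi-2.

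**Step 5: where the gain comes from.** Fisher's and Chi-2 use the same 2x2 table, so their difference reflects Fisher's conservatism alone. At HR 3 without dropout that is 35.7 - 20.3 = 15.4 points. Moving from Chi-2 to the permutation log-rank adds the event times, which here contribute 34.8 - 35.7 = -0.9.

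**Step 6: cross-check.** Schoenfeld's formula is power = Φ(√(d·p·q)·|ln HR| - 1.96). With d = 8.5, p = 0.35, q = 0.65 and HR 3, √1.934 x 1.099 - 1.96 = -0.43, giving 33.3%. This is close to the permutation result of 34.8%.

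**The case against.** The strongest reply is that power is not this plan's criterion. The study is descriptive, has no formal hypotheses and sets no significance level, and section 7.4 introduces subgroup work as optional. That stands. It limits the point to an exploratory comparison, and the plan contains no rule by which a non-significant result would be declared to show no difference. At 70% survival and HR 2 to 4, ordinary log-rank power is itself only about 15 to 60%.

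A reader might infer that ignoring event times is what costs the power. The working does not support that: most of the gap is Fisher's discreteness, and against uncorrected Chi-2, which section 7.4 names first, the log-rank is roughly level.

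A reader might also infer that this comparison decides how the US early feasibility data are pooled. Section 7.4 says only that the exclusion of dialysis patients from that study will be taken into account when pooling.

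Nor does the plan assign amputation-free survival to Chi-2 or Fisher's by name. That follows from the percentage definition in section 18, because no other listed test fits a percentage.

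Finally, loss may be small. Sections 6.3.4 and 6.4.4 require phone calls, a letter and contact with the general practitioner first, and death and major amputation are known at exit. This reduces the number of subjects with unknown status but does not define how to count those who remain, and it does not cover the 30-day exits.

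**Conclusion.** The point holds as a cheap improvement. The firm part needs no assumed rates: the plan commits to a comparison that covers its primary endpoint, offers only yes/no tests for it, and leaves the status of partly observed subjects undefined although event dates are collected.

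The size depends on assumptions. At 20 subjects, a permutation log-rank gains about 5 to 24 points over Fisher's and about -3 to +9 over uncorrected Chi-2. These ranges depend on the assumed survival, hazard ratio, split, dropout and coding of dropouts. They should not be read as the cost of discarding event times, and with any test a non-significant result here would say little at moderate effects.

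**What to change.** In section 18, define amputation-free survival as the time from the procedure to the first of death or major amputation of the treated limb. Subjects lost, withdrawn or exited early, including after failed implantation, are censored at last known status.

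In section 7.4, add a time-to-event class. By dialysis status, report Kaplan-Meier estimates at twelve months with 95% confidence intervals as the main output, plus a log-rank test with a permutation p-value labelled exploratory. Keep Chi-2 or Fisher's for truly binary parameters such as technical success.

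In any analysis pooled with the early feasibility study, note that all dialysis subjects come from this study, so dialysis status is partly confounded with study. Show the comparison within this study alone as well.

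The cost is a few sentences and a short script, possibly outside SPSS, with no new data, visits or subjects. There are two limits. The log-rank test loses some power if hazards cross. Censoring also assumes that those who leave have the same outlook as those who stay, which is doubtful after failed implantation, so the number censored for that reason should be shown by group.
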